1. INTRODUCTION

1.1.Background and Rationale

Eosinophilic oesophagitis (EoE) is an antigen-mediated, inflammatory condition with a prevalence of 10-40/100,000 people in Europe¹. Though rare, incidence is increasing, in keeping with trends seen in other allergic conditions such as asthma². Whilst increased awareness results in better recognition, the increasing prevalence of EoE exceeds this explanation^{1,3}. EoE frequently presents as dysphagia, often with food bolus obstruction, which can lead to emergency hospital admissions. Others present with treatmentresistant chest-pain and heartburn. The cause of varied symptoms in EoE is a hot topic of debate. Diagnosis is based on histological assessment of eosinophil infiltration of the oesophageal mucosa and index oesophageal symptoms. Despite histological remission in 90% of cases after treatment, at least 30% of patients remain symptomatic^{4,5}; however, currently there are no methods of investigating these symptoms further within routine care pathways. EoE is a chronic condition, managed primarily with medical treatment, i.e. topical steroids or proton pump inhibitors, or food elimination diets. In non-responsive cases, oesophageal dilation is required². This latter approach carries a non-trivial risk of side effects including bleeding and oesophageal perforation. Additionally, EoE is associated with increased demand on endoscopy units, with 25% of individuals undergoing endoscopy for food bolus obstruction, presenting with EoE².

These observations highlight limitations of current assessment and management of EoE, a condition that carries significant quality of life (QOL) burden for affected individuals, including difficulties coping with symptoms of unknown cause, challenges with eating and subsequent impact on social interactions⁶. Individuals with EoE responding to a survey I conducted voiced that they felt the condition is poorly understood, live with "fear of making mistakes" and feel frustrated due to a "lack of information". Although it is known that symptoms in EoE occur for various reasons, the causes of symptoms are often not assessed, with emphasis on histology and endoscopic appearance. With global movement towards precision medicine and patient-directed therapy, this work will explore how assessments of oesophageal motility and function may be used to define pathophysiological processes that cause patient symptoms in EoE. Oesophageal physiology investigations are used routinely to diagnose primary motility disorders and gastro-oesophageal reflux disease (GORD); however, their role in EoE is undefined. If these tools were deemed informative for EoE, they could enable future treatment to be targeted at specific disease manifestations.

This feasibility research will focus on four problems not addressed by current EoE management:

- 1. Oesophageal motility has not been formally studied when individuals with EoE swallow food. This may provide much-needed explanation for symptoms that persist despite histological remission.
- 2. Monitoring of treatment response requires invasive, expensive interventions using endoscopy. Alternative approaches to monitor EoE may reduce patient burden and strain on endoscopy units.

- 3. Patient acceptability of interventions used to monitor EoE is unknown.
- 4. The relationship between objective investigation results, reported symptoms and changes in response to treatment are poorly understood.

2. STUDY OBJECTIVES

2.1.Research Aim

To assess the use and acceptability of physiological investigations of oesophageal function in understanding symptoms in EoE and to assess the relationship between physiological parameters, symptom profiles and response to treatment.

2.2.Objectives

The feasibility of a more comprehensive approach for the assessment of EoE using physiological investigations of oesophageal function will be assessed with the following objectives:

- 1. Describe oesophageal motility in EoE when solid food is swallowed and assess motility during symptomatic episodes that occur contemporaneously during eating.
- 2. Evaluate an alternative method of measuring response to treatment in EoE using the parameter mean nocturnal baseline impedance (MNBI), obtained during 24 hour ambulatory pH/impedance monitoring.
- 3. Determine the feasibility of performing oesophageal physiology investigations within the patient pathway and understand challenges associated with acceptability using qualitative interviews.
- 4. Describe the relationship between physiological assessments, symptom profiles, parameters from routine clinical care and changes following a treatment period.

3. STUDY DESIGN

3.1.0verview

A dual-site exploratory, mixed-method feasibility study comprising a serial diagnostic observational study with embedded qualitative design⁷.

[figure not shown]
The sites are:

- County Durham and Darlington NHS Foundation Trust (CDDFT)
- University College London Hospital NHS Foundation Trust (UCLH)

Three elements (high-resolution manometry (HRM), pH/impedance monitoring and qualitative interviews) will be completed in a longitudinal format with 3 overlapping phases, with a recruitment and data collection period of 21 months. Eligible patients will be identified by lead Consultants at CDDFT or UCLH, with initial study participation for those with a new diagnosis within a 3-week period, prior to standard care treatment initiation.

3.2.Study Flow Chart

Sponsor No. 10091 – Protocol - v1.1 – 2022.10.05 IRAS ID: 299013

3.3.Schedule of events

	1) Outpatient appointment	2) Checking eligibility	3) Discussion with potential participant	4) Appointment scheduled at local site	5) Visit 1
What will happen?	 □ Patient identified as potentially eligible □ Patient accepts patient information sheet (PIS) and is willing to be contacted by telephone to discuss the project □ Patient does not accept PIS. Asked if willing to answer question on reason for not wishing to participate. □ If yes, written response obtained 	Pre-screen confirmation of eligibility using medical records	□ Patient contacted a minimum of 48 hours after being given PIS □ Project discussed □ Eligibility discussed □ Patient accepts or declines participation Declines: □ Willing to answer question on reason for not wishing to participate? □ If yes, transcribe this Accepts: □ Appointment date to be scheduled for visit 1	□ Date established with return visit next day □ Pre-test preparation explained: ○ PPI – stop 1 week before ○ Anti-histamine – stop 3 days before ○ Other antacids – stop 24-hours before ○ Fast for 4 hours before tests	□ Written informed consent ○ Physiology ○ Qualitative □ Participant completes 3 questionnaires □ HRM Study as per local SOP □ Start of 24-hour pH/impedance study as per local SOP □ Clinical information relevant to study documented (including endoscopy & biopsy results)
Who?	PI (Consultant Gastroenterologist)	Researcher (CI)	Researcher (CI)	CDDFT: Researcher (CI) UCLH: Administrative Staff or local Clinical Scientist/GI Physiologist	CDDFT: Researcher (CI) UCLH: Clinical Scientist/GI Physiologist
Where?	Outpatient Gastroenterology appointment at CDDFT or UCLH	Computer based admin task. Documented in pre-screen log	Telephone conversation	Telephone conversation	CDDFT: Medical Physics department, UHND UCLH: GI Physiology Unit, UCLH

	6) Visit 2 (day after visit 1)	7) Results discussion	8) Qualitative interview arranged	9) Visit 3	10) Repeat physiology appointment scheduled at local site	11) Visit 4 (2-4 months post-treatment)	12) Visit 5 (day after visit 4)
What will happen?	pH/ impedance monitor and diary sheet returned	Major results contextualised with patient	Qualitative interview scheduled in participants' preferred medium (telephone, video call, face to face)	Qualitative interview	□ Date established with return visit next day □ Pre-test preparation explained: ○ PPI – stop 1 week before ○ Anti-histamine – stop 3 days before ○ Other antacids – stop 24-hours before Fast for 4 hours before tests	□ Participant completes 3 questionnaires □ HRM Study as per local SOP □ Start of 24-hour pH/ impedance study as per local SOP	□ pH/impedance monitor and diary sheet returned
Who?	CDDFT: Researcher (CI) UCLH: Clinical Scientist/GI Physiologist	Consultant Gastro- enterologist at local site	Researcher (CI)	Researcher (CI)	CDDFT: Researcher (CI) UCLH: Administrative Staff or local Clinical Scientist/GI Physiologist	Researcher (CI)	Researcher (CI)
Where?	CDDFT: Medical Physics department, UHND UCLH: GI Physiology Unit, UCLH	Outpatient appointment /Telephone	Telephone	☐ Teleph one ☐ Video call ☐ Face to face	Telephone conversation	CDDFT: Medical Physics department, UHND UCLH: GI Physiology Unit, UCLH	CDDFT: Medical Physics department, UHND UCLH: GI Physiology Unit, UCLH

IRAS ID: 299013

3.4.Practicalities

3.4.1. Setting up sites

Feasibility reviews will be conducted at CDDFT and UCLH to ensure confirmation of capacity and capability, once national regulatory approvals are received. Each site (CDDFT and UCLH) will have a site visit prior to study commencement with PI (lead Consultant) present. The suitability of the two sites and formal decision for inclusion in the study will be documented in the trial master file. The CI and research fellow ([name]) will liaise with the two sites on a regular basis. The trial master file and individual site files will be created.

3.4.2. Participation

Participants will be asked to give consent to participate in Oesophageal Physiology investigations (HRM & pH/impedance monitoring) and to be interviewed separately. However, certain study elements are pre-requisites to others (see section 3.5).

Recruited patients will be reimbursed for travel to and from sites for study involvement.

3.5.Investigations

The acceptability and practicability of carrying out physiological assessments in EoE will be evaluated across the study. Limited efficacy testing will also be used to gain insight into the potential value of physiological tests (HRM and pH/impedance monitoring). A qualitative approach will explore the broader picture of the role of diagnostic assessments in EoE and also patient experiences of living with this chronic condition.

3.5.1. High-resolution manometry (HRM)

The use of advanced tests of oesophageal function in EoE will be assessed. High-Resolution Manometry (HRM) with a solid test meal will be compared with standard testing with water swallows⁸. Assessment will be made before and after therapy. Patient Reported Outcome Measures (PROMs), using validated questionnaires for benign oesophageal motility disorders will be used to assess overall symptoms⁹⁻¹¹, in addition to assessment of contemporaneously occurring symptoms during HRM testing.

3.5.2. pH/impedance monitoring

The use mucosal impedance measurements in monitoring EoE status will be evaluated, before and after standard therapy, with patients undergoing tests directly following HRM. Mucosal impedance will be measured to assess its practicability as a marker of mucosal integrity during quiescent nocturnal periods. Evaluation of gastro-oesophageal reflux burden will also be assessed¹².

Participation in HRM is a pre-requisite of pH/impedance monitoring.

IRAS ID: 299013

3.5.3. Qualitative interviews

The acceptability of tests used in EoE and also the wider context of living with EoE will be explored using qualitative interviews.

Purposive sampling will be used to recruit participants, reflecting a diverse cohort of individuals accounting for different demographics, genders, age and ethnicity. This will enable exploration of cultural differences regarding the impact of living with this rare, chronic disease and the value placed on investigations for monitoring EoE. Sampling will also acknowledge diagnosis history, reflecting those with a new diagnosis and those with treatment refractory disease (defined in section 4.2) to ensure that interviewees represent individuals at different points within the patient journey.

Interviews will commence between initial and repeat physiology tests (during treatment period). This will capture people when they have first-hand experience of the tests and the available treatment options, thus providing an opportunity to explore people's views on their short-term management. Participation in at least one physiological assessment (HRM) is therefore required for participation in a qualitative interview. Participants will have received the results from their initial HRM and pH/impedance investigations prior to interview.

3.6.Planned recruitment

60 patients (30/site) will be recruited. Initial investigations at UCLH will be conducted by a local Clinical Scientist, ensuring a timely approach. The study research fellow will perform post-treatment investigations at UCLH during planned visits, enabling multiple patients to be seen on a single day. Major results/findings from HRM and pH/impedance studies will be discussed and contextualised with patients once formally reported.

Qualitative interviews will be conducted with a subset of 20 recruited patients following initial HRM and 24-hour ambulatory pH/impedance investigations. Individuals declining participation will be asked if they would be willing to answer an open-ended question on reasons for not wishing to participate, with consent sought to use responses anonymously to further understand acceptability.

3.7. Patient Public Involvement

A PPI advisory group comprising 5 adults, 3 with experience of EoE, one without lived experience of the condition and the founder of the national UK EoE charity (EOS Network) has been convened. The direct experience of EoE for the majority of the group will be used to optimise the project. One challenge of this project may be recruitment, due to requirements to attend additional hospital appointments to undergo invasive tests. The advisory group's own experiences of diagnostics surrounding EoE will be drawn upon to address this.

Meetings will be quarterly and predominantly carried out via video conference, with one annual face-to-face meeting per year. Individuals will be reimbursed for involvement as per NIHR guidance. Individuals can choose their preferred form, ensuring no-one is

excluded from participation due to issues surrounding payment. The role of the advisory group will evolve during the course of the project; however, anticipated roles are:

- Advising on development of patient information leaflets
- Discussing recruitment barriers and ways to approach this
- Contribution to writing/design of the interview guide
- Study management
- Identification of important areas for analysis
- Raising awareness of the study and dissemination
- Contributing to study outputs e.g. conference presentations and talks for members of the EoE community, ensuring outcomes are presented effectively.

An initial meeting with the PPI advisory group will provide training and support for involvement.

4. STUDY POPULATION

4.1. Number of participants

Recruitment aim of 60 patients (30/site). 20 of these participants will be recruited to semi-structured, qualitative interviews.

4.2.Inclusion criteria

Patients from CDDFT or UCLH with:

- New diagnosis of EoE (>15/high-powered field (hpf) or 0.3mm² on oesophageal biopsy and index oesophageal symptoms).
- Known diagnosis of EoE (current histological and symptom status documented but does not impact inclusion).

4.3. Exclusion criteria

- <18 years old

- Current involvement in a Clinical Trial of an Investigational Medicinal Product (CTIMP) for EoE.
- Eosinophilia as a result of other known cause (local or systemic)
- Oesophageal stricture on oesophago-gastric duodenoscopy
- Previous upper GI surgery
- Active comorbidity including: Barrett's oesophagus, oesophageal varices, coagulation disorders
- Significant nasopharyngeal pathology, preventing nasogastric intubation
- Opiate use
- Unable to provide informed consent
- Limited verbal communication
- Non-English language speaker

5. PARTICPANT SELECTION AND INFORMED CONSENT

5.1. Identifying Participants

Eligible patients will be identified by lead Consultants/PI at CDDFT or UCLH who will discuss research participation with the patient initially and provide the Patient Information Sheet (PIS) and a copy of the consent form if the patient is willing to consider participation. The PI will inform the research fellow of patients interested in being contacted about the study.

Prior to contacting the patient, the research fellow will use the patient's medical records to ensure study eligibility is met from a medical perspective. The research fellow will then contact the patient after a minimum of 48 hours, to ensure the participant has had time to read the PIS and discuss with others if desired. If the individual chooses to participate, an appointment will be scheduled with the participant. For those with a new diagnosis of EoE, initial study participation would occur within a 3-week period to prevent significant delay to standard care treatment initiation which would be paused until after initial tests. Those with a known EoE diagnosis would be scheduled for physiology testing after a minimum of 2 months following initiation of EoE specific treatment. Patients will be asked to stop proton pump inhibitors (if taking) for 1 week prior to physiological tests; however, stopping for 3 days will be accepted.

Individuals declining participation will be asked if they would be willing to answer an open-ended question on reasons for not wishing to participate, with consent sought to use responses anonymously to further understand acceptability.

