6. STUDY PROCEDURES

6.1.Covid-19 (Sars-CoV-2)

Local regulations (CDDFT and UCLH) will be adhered to regarding the Covid-19 pandemic.

6.2.Pre-treatment tests

IRAS ID: 299013

6.2.1. Visit 1

PROMs will be collected using three validated questionnaires completed by the patient. These will assess dysphagia, reflux burden and oesophageal hypervigilance and anxiety using the Brief Esophageal Dysphagia Questionnaire/BEDQ¹⁰, Reflux Disease Questionnaire/RDQ¹¹ and Esophageal Hypervigilance and Anxiety Scale/EHAS⁹ respectively.

HRM: HRM involves placement of a nasogastric catheter. Testing will follow standard procedures with additional provocation tests:

- Assessment of 5 mL water swallows
- Rapid drink challenge 200 mL water drunk continuously through a straw. This is used to further assess lower oesophageal sphincter relaxation and oesophageal body pressurisation
- Solid test meal 200g rice eaten to assess oesophageal function using a physiologically relevant test meal

Symptomatic episodes during swallowing will be recorded to determine if reported symptoms correspond with abnormal HRM events, thus assessing the clinical relevance of motility findings. Findings will be classified using the Chicago Classification (CCv4.0)⁸.

pH/impedance monitoring: Following PROMs and HRM, 24-hour ambulatory pH/impedance monitoring using a nasogastric catheter will commence. This involves placement of a second naso-gastric pH/impedance catheter. Testing will follow standard procedures. Patients will be provided with a paper diary to complete and an explanation will be given as to how to use the ambulatory recorder.

6.2.2. Visit 2

Participants will return the ambulatory recorder the following day (24 hours after initiation of ambulatory pH/impedance test).

Individuals will begin treatment course after physiology tests have been performed. Treatment will be standard care (usually locally acting steroids and/or proton pump inhibitors), decided upon by patient and clinician (study does not influence treatment choice). Those patients with an established diagnosis of EoE who are in symptom remission may not begin new treatment course and in this case would only participate in initial tests.

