6.3. Qualitative interviews

6.3.1. Visit 3

Qualitative interviews: Semi-structured interviews will be conducted in a sub-set of patients in their preferred medium (telephone/video-conference call/face to face (Sars-CoV-2 permitting)) with support provided. Audio recordings will be made with consent

IRAS ID: 299013

and transcribed verbatim, forming the basis for analysis. Interviews will commence between pre- and post-treatment HRM and pH/impedance tests.

An iterative approach will be taken during the interview process, with data collection and preliminary coding of themes and subthemes to enable the integration and refinement of occurring themes into subsequent interviews.

6.4.Post-treatment tests

6.4.1. Visit 4

HRM: PROMs and HRM will be repeated as described in pre-treatment tests (6.2), two-four months following a course of treatment, to assess physiological changes. Around a similar time, participants will also receive repeat endoscopies with biopsies and clinical assessment as part of standard care.

pH/impedance monitoring: 24-hour ambulatory pH/impedance measurements will be repeated as described in pre-treatment tests (6.2), two-four months following a course of treatment, to assess physiological changes. Again, this will be performed after repeat HRM study. However, should a patient withdraw consent to repeat HRM but wish to repeat the 24-hour ambulatory pH/impedance study, this is acceptable.

6.4.2. Visit 5

Patients will again be required to return the ambulatory recorder 24 hours after the initiation of the pH/impedance test.

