16. APPENDIX

16.1. Brief Esophageal Dysphagia Questionnaire

Brief Esophageal (oesophageal) Dysphagia Questionnaire

We would like to ask about your dysphagia (difficulty swallowing) symptoms over the past 2 weeks (14 days) and two experiences over the last 12 months. Please think about your symptom experiences and choose the best answer.

Over the past 14 days, on average, how often have you had the following? If your response falls between two categories, please make your best guess. If you are unable to eat the type of food in the question, please choose "Cannot eat this". Please place a tick in the relevant box.

		0	1	2	3	4	5
	Cannot Eat This	Rarely/ Never	Once or twice a month	1-2 times per week	3-5 times per week	Daily or almost daily	Several times per day
Trouble eating solid food (meat, bread, vegetables)				·			
Trouble eating soft foods (yogurt, jelly, pudding*)							
Trouble swallowing liquids							
Pain while swallowing	-						
Coughing or choking while swallowing foods or liquids	-						

Over the past 14 days, on average, how would you rate your discomfort or pain during swallowing? If you are unable to eat the type of food, please choose "Cannot eat this".

	Cannot Eat This	0 None	1 Very Mild	2 Mild	3 Moderate	4 Moderately Severe	5 Severe
Eating solid food (meat, bread, vegetables)							
Eating soft foods (yogurt, jelly, pudding*)							
Drinking liquids							

^{*}Pudding refers to a soft dessert such as mousse

Approximately how many times in	the past 12 months have you -	
Had food stuck in your throat or o Had to visit the emergency room* *Accident and Emergency Department,	because of food stuck in your thr	
Participant Initials	Screening Number	Participant Number

IRAS ID: 299013

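### In PPI-treated patients the Visit 4 questionnaires are completed after the PPI has been stopped for the tests, so PROM change cannot be read as on-treatment symptom response

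*Protocol*

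**What the plan says.** **Treatment.** Section 6.2.2 describes standard-care treatment as "usually locally acting steroids and/or proton pump inhibitors", chosen by patient and clinician.

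**Test preparation.** Section 5.1 has patients "asked to stop proton pump inhibitors (if taking) for 1 week prior to physiological tests; however, stopping for 3 days will be accepted". In section 3.3 the preparation list appears twice, at step 4 (before Visit 1) and step 10 (before Visit 4). Each time it reads "PPI – stop 1 week before" and does not mention the 3-day allowance. No stop is listed for locally acting steroids.

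**Questionnaire timing.** Section 3.3 lists under Visit 4: "Participant completes 3 questionnaires". Section 6.4.1 states: "PROMs and HRM will be repeated as described in pre-treatment tests (6.2), two-four months following a course of treatment". The order within the visit comes from section 6.2.1: "Following PROMs and HRM, 24-hour ambulatory pH/impedance monitoring using a nasogastric catheter will commence". The forms are therefore filled in after the PPI has been stopped.

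**Recall windows.** The BEDQ (16.1) covers "symptoms over the past 2 weeks (14 days) and two experiences over the last 12 months". The RDQ severity items (16.2) ask about the past week; the stem of the RDQ frequency items is cut in the text at hand. The EHAS (16.3) asks about the past month.

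**Use of the scores.** Objective 4 (section 2.2) concerns symptom profiles and what changes after a treatment period. Section 8.2.4 collates PROM symptom type and severity with physiology, endoscopy and histology in relation to treatment. Sections 8.2.1 and 8.2.2 describe HRM and mucosal impedance differences in relation to overall symptom status from the PROMs.

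**The concern.** A post-treatment symptom score is normally taken to show how the patient feels on the treatment. Here one of the usual treatments is withdrawn for the tests, and the questionnaires asked on the test day look back over a period that includes the withdrawal. For the RDQ severity items the requested stop and the recall window have the same length.

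The score that enters Objective 4 and section 8.2.4 as a post-treatment value may then describe, in part or in whole, days without the PPI. The 3-day allowance means this part can differ from patient to patient, and between Visits 1 and 4 in the same patient. The protocol does not say that the actual number of days off PPI is recorded, does not ask for any questionnaire before the stop, and does not tell patients to answer for their on-treatment period. No later analysis can recover on-PPI symptoms that were never asked about.

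**Working it through.** The plan gives no figure on this point to reproduce. The check is a count of days.

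**Inputs**
- Stop length s: 7 days (sections 3.3 and 5.1) or 3 days (accepted in section 5.1).
- Recall window w: RDQ severity 7 days (16.2); BEDQ 14 days (16.1); EHAS past month (16.3), taken here as 28 to 30 days.

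**Formula.** Days off PPI in the window = min(s, w). Share off PPI = min(s, w) / w. The form is assumed to be completed on the day of the test, at the end of the stop.

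| Questionnaire | Window | 7-day stop: off / on | Share off | 3-day stop: off / on | Share off |
|---|---|---|---|---|---|
| RDQ severity | 7 | 7 / 0 | 7/7 = 100% | 3 / 4 | 3/7 = 43% |
| BEDQ | 14 | 7 / 7 | 7/14 = 50% | 3 / 11 | 3/14 = 21% |
| EHAS, 30-day month | 30 | 7 / 23 | 7/30 = 23% | 3 / 27 | 3/30 = 10% |
| EHAS, 28-day month | 28 | 7 / 21 | 7/28 = 25% | 3 / 25 | 3/28 = 11% |

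Under the requested stop the RDQ severity window contains no on-PPI day. Under the accepted minimum it contains four.

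**BEDQ 12-month counts.** The two 12-month items have the reverse problem: their window reaches back past the start of treatment. If Visit 4 falls 2 to 4 months after treatment starts, the part of the window before treatment is (12 − 2)/12 = 83% to (12 − 4)/12 = 67%. Counting from treatment start is an assumption. Section 6.4.1 counts from a course of treatment without saying whether that means its start or its end, while section 3.5.3 places the interval between the two test rounds within the treatment period.

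**Visit 1.** The same stop applies at step 4. Under section 5.1, patients with a known diagnosis are tested after at least 2 months of EoE treatment. If that treatment includes a PPI, their Visit 1 scores carry the same off-PPI shares. Newly diagnosed patients have treatment paused until after the initial tests, so an untreated baseline is intended for them.

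**The case against.** **The off-PPI state is a standard condition.** HRM, reflux testing and questionnaires are taken together in the same state at both visits, and Objective 4 asks how symptoms relate to physiology. Simply moving the questionnaires earlier would pair on-PPI symptoms with off-PPI reflux and impedance results. Symptoms noted during HRM do not replace RDQ reflux burden for that purpose. This stands, and it is a reason to add a set rather than move one. It does not rescue the Visit 4 set as a measure of response to treatment.

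**A reader might infer that symptom response in PPI-treated patients is hidden altogether.** The documents do not support that. With the 3-day stop, four of seven RDQ days are on PPI. The BEDQ window keeps 7 to 11 on-PPI days and the EHAS window 21 to 27. A patient on a steroid as well as a PPI is off the PPI but, as far as the listed stops go, not off the steroid. Any PPI effect that outlasts the stop would still show.

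**A reader might also infer a false difference between PPI and steroid treatment.** No such comparison is planned in section 8.2, treatment choice is outside the study's control, and patients on both treatments stop the PPI too. What is planned is a descriptive collation in relation to treatment.

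**It is a feasibility study with descriptive outcomes.** That lowers the stakes. But section 8.2.4 is meant to show whether meaningful data of this kind can be collected, and questionnaire timing is part of that question.

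**Conclusion.** The point holds for patients whose treatment includes a PPI. Their Visit 4 scores are taken with 3 to 7 of the 7 RDQ severity days, 3 to 7 of the 14 BEDQ days and 3 to 7 of the 28 to 30 EHAS days off PPI. PROM change after treatment therefore cannot be read as on-treatment response in these patients: the RDQ may largely or wholly miss it, and the BEDQ and EHAS may dilute it. The varying stop length adds a difference between patients and visits that, without a record, cannot be described.

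These figures are shares of recall days, not a bias in any score. How far a score shifts depends on how quickly PPI benefit fades after stopping and on how many participants take a PPI; the protocol gives neither. The RDQ figure rests on the severity items alone. The conclusion assumes that patients follow one of the two stated stop lengths and answer for the window printed on the form.

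The point is worth correcting before data collection, because the missing information cannot be recovered afterwards and the correction is small.

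**What to change.** - Leave the test preparation as it is.
- At the step 10 scheduling contact, issue the PROMs (at least the RDQ and BEDQ) to every participant due for Visit 4, for completion before any PPI is stopped. Use this set to describe symptom response to treatment.
- Keep the Visit 4 set and use it to relate symptoms to same-day, off-PPI physiology. State in section 8.2 which set serves which purpose.
- Record the actual number of days off PPI at Visits 1 and 4 in the case report form.
- Keep the Visit 1 questionnaires at Visit 1. Section 5.3.1 places written consent there, before any study procedure, so an earlier set would need earlier consent. Interpret the baseline using the recorded days off PPI, particularly in patients already on a PPI.
- Do not use the two 12-month BEDQ items as a pre/post change, because their window reaches well before treatment.
- Reconcile section 3.3 (one week only) with section 5.1 (one week, 3 days accepted). No view is taken here on which stop length is right.

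The cost is one extra short set of forms per participant before Visit 4, one added field at each test visit and a small amendment. Consent is already in place by step 10. The extra set describes the period before the stop rather than the test day, which is why the Visit 4 set stays.
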